Statement of problem: There is a strong crossway relationship between periodontitis and hypertension. Hypertension is the most prevalent of cardiovascular diseases and its prevalence is increased by the presence of periodontitis. Periodontal attachment loss is higher in hypertension patients when compared to healthy subjects. Both are examples of non-communicable diseases (NCDs), also known as chronic inflammatory diseases, they tend to be of long duration and are the result of a combination of genetic, physiological and environmental factors. The lack of an appropriate balance between these factors results in cellular changes as well as the levels of cytokines with subsequent changes in clinical manifestations of periodontal diseases. Both periodontitis and hypertension are associated with inflammation and an increase in specific proinflammatory cytokines.

Aim of the study: To investigate the correlation between the clinical parameters and the levels of Endocan and TNF- α in gingival crevicular fluid (GCF) before and after non-surgical periodontal therapy (NSPT) in stage II periodontitis patients with hypertension in comparison to non-hypertensive patients.

Materials and Methods

Clinical assessment of specific clinical parameters: plaque index, gingival index, probing depth, clinical attachment level (CAL) as primary outcome. Biochemical assessment of Endocan and TNF- α levels in GCF by Enzyme Linked Immunosorbent Assay (ELISA) as well as measurement of blood pressure at baseline and after 3 months as secondary outcomes.

II. Background:

Hypertension and periodontitis are part of a group of diseases called non-communicable diseases (NCDs), which are rising in prevalence due to an increasingly aging population. NCDs comprise 71% of global death.

Hypertension is defined as repeated office SBP values ≥ 140 mmHg and/or DBP ≥ 90 mmHg. It is a multifactorial disease, that can be caused by endothelial dysfunction (ED), oxidative stress, and inflammation. Periodontitis is a chronic multifactorial inflammatory condition affecting the tooth periodontium. In periodontitis, chronic inflammation occurs in reaction to untreated bacteria, and this is associated with continuous stimulation of the immune system which subsequently causes damage to the tooth supporting tissues. The damage is manifested clinically with gingival bleeding, foul odor, clinical attachment loss, tooth mobility and may lead eventually to tooth loss.

The interaction between bacteria and host immune responses is the link between periodontitis and hypertension along with a number of chronic systemic diseases, such as diabetes mellitus, other CVDs and neurological diseases such as Alzheimer.

Patients with periodontitis often present with higher arterial BP values and a 30% to 70% higher chance to also present with hypertension, especially when there is active gingival inflammation.

Periodontitis patients express elevated levels of local and systemic inflammatory biomarkers, such as C-reactive protein (CRP), TNF- α , neutrophilic enzymes, WBCs, disparity in T-cell subtypes, neutrophil dysfunction, which are all mechanisms resulting in vascular changes and endothelial dysfunction (ED).

The presence of periodontal pathogens has been linked to hypertension in epidemiological studies. Periodontal pathogens cause prolonged T-cell activation and elicited increased levels of CRP, TNF- α , and IL (interleukin)-1 β , resulting in an increased BP.

The first study to suggest a correlation between periodontal pathogens and hypertension was INVEST (infections and vascular disease epidemiology study) in 2012, its results concluded a direct relationship between the levels of subgingival periodontal bacteria and both systolic blood pressure (SBP) and diastolic blood pressure (DBP) as well as hypertension prevalence.

Endothelial Dysfunction (ED) is one of the early signs of hypertension, Endocan is a biomarker of ED, it also plays a role in endothelium-dependent pathological disorders including cardiovascular diseases (CVDs) and periodontitis. This was the trigger to suggest Endocan as a clinical biomarker for hypertension in 2013.

A consensus report in 2020 showed that there is evidence from epidemiological studies that periodontitis patients exhibit significant endothelial dysfunction, measured by flow-mediated dilation (FMD), arterial stiffness (e.g., pulse wave velocity—PWV) and a significantly greater thickness of the carotid intima media (cIMT) and elevated arterial calcification scores. This explains why both periodontitis and hypertension are correlated by endothelial dysfunction.

Endocan, previously known as Endothelial cell-specific molecule-1 (ESM-1) is one of the molecules secreted by endothelial cells. Endocan is a 50 kDa soluble proteoglycan that regulates many major cellular activities like cell differentiation, cell proliferation, VCAM-1 and ICAM-1 expression, regulation of leukocyte migration, neovascularization, and metastasis of tumors.

Endocan was recognized of being overexpressed in inflammatory conditions, CVDs, sepsis, cancer, and obesity along with increase in the secretion of vascular cell adhesion molecule-1 (VCAM-1), E-selectin, and intercellular adhesion molecule-1 (ICAM-1). Therefore, Endocan has been designated as a proinflammatory mediator that binds to Lymphocyte function-associated antigen-1 (LFA-1) on human leukocytes and regulates LFA-1 interactions with ICAM-1. Previous evidence indicates that Endocan is increased in inflammatory diseases and inflammation has already been shown to have an important contributing part in the pathogenetic changes in both periodontitis and hypertension.

Serum Endocan levels were significantly higher in the HT group ($P < .001$). Also, it correlated positively with carotid intima-media thickness (cIMT), and high-sensitivity C-reactive protein (hsCRP) which are pathological indicators of atherosclerosis and hypertension.

A systematic review conducted from 20 studies in 2023, showed that in hypertensive patients circulating Endocan levels are significantly elevated. Thus, suggesting endocan as an easy-to-use biomarker to detect ED in hypertension.

According to **Armitage 1999**, Periodontitis was classified into chronic, aggressive, necrotizing ulcerative periodontitis and periodontitis as a manifestation of systemic disease. However, a new system of periodontal classification has been adopted, in which the types of disease that were previously identified as "chronic" or "aggressive" are now classified under one category ("periodontitis") and re-diagnosed based on many variants (staging and grading system)

The stage is based on the severity of the disease and the complexity of the disease management (in terms of loss of clinical attachment between teeth, radiographic bone loss, and tooth loss), complexity and distribution. Grading provides additional information about the biological features of the disease, including history-based analysis of the progression rate of

periodontitis; progression risk assessment; analysis of possible adverse effects of treatment; and risk assessment that the disease or its treatment may adversely affect the patient's normal life.

Periodontitis is described in four stages ranging from Stage I: Initial periodontitis (CAL 1-2mm), Stage II: Moderate periodontitis (CAL 3-4 mm), Stage III: Severe periodontitis with potential for loss of dentition due to periodontitis (<4), and (CAL ≥ 5 mm) Stage IV: Severe periodontitis with potential for loss of dentition due to periodontitis (≥ 5) and (CAL ≥ 5 mm). Grading focuses on assessing risk factors like smoking, diabetes, and outcomes of scaling and root surface debridement. Grade A: Slow rate of progression (no CAL loss over 5 years), Grade B: Moderate rate of progression (CAL loss <2 mm over 5 years), and Grade C: Rapid rate of progression (CAL loss ≥ 2 mm over 5 years).

Non-surgical periodontal therapy (NSPT) is the “gold standard” therapy for periodontal diseases. NSPT aims at mechanical removal of bacterial plaque from the tooth surface. NSPT results in reduction of the microbial load in periodontal pockets favoring the presence of gram-positive bacteria and reducing gram-negative bacteria. Also, NSPT results in reducing the levels of proinflammatory cytokines.

In a study conducted by **Kumar in 2020**, There was a significant reduction in the Endocan ($p < 0.01$) among all the groups after NSPT. This study also suggested that Endocan levels might be increased in periodontal disease and decreased after periodontal treatment.

On the other hand, there is limited evidence that NSPT could improve arterial blood pressure, but many studies appear to support a positive correlation between severe periodontitis and hypertension. Patients with periodontitis exhibited higher mean SBP and DBP when compared with non-periodontitis patients. Also, prevalence of hypertension is higher in periodontitis patients. Systemic biomarkers like CRP, TNF- α and IL (interleukin)-1 β and Endocan were elevated in patients with hypertension and periodontitis. Periodontal attachment loss was higher among hypertensive patients in comparison to non-hypertensive patients.

To the best of our knowledge, no previous study correlated between clinical parameters and the levels of Endocan and TNF- α before and after NSPT in stage II periodontitis in individuals with controlled hypertension in comparison to healthy (non-hypertension) individuals.

III. Research Question

“What is the effect of NSPT on the clinical periodontal parameters and its correlation to changes in GCF levels of Endocan and TNF- α in hypertensive periodontitis patients compared to non-hypertensive patients?”

PICOTS Elements:	
Patient/Problem	Stage II periodontitis patients with controlled hypertension.
Intervention	Non-Surgical periodontal therapy.
Comparator	Stage II periodontitis healthy individuals.
Outcome	-Clinical evaluation as a primary objective. -Biochemical evaluation as secondary objective. -Blood pressure measurement as secondary objective.
Time	-Baseline and 3 months (for clinical evaluation) -3 months (for biochemical analysis) -3 months (for blood pressure evaluation)
Setting	Faculty of Dentistry, Ain Shams University.

IV. Aim of the Study:

- 1- To correlate changes in GCF level of Endocan and TNF- α with changes in periodontal parameters after NSPT in both groups with clinical parameters.
- 2- The aim of the present study is to investigate changes in the levels of Endocan and TNF- α in stage II periodontitis patients with controlled hypertension in comparison to healthy subjects before and after NSPT.
- 3- To correlate blood pressure changes before and after NSPT.

Primary outcome:

Clinical evaluation of periodontal parameters plaque Index, gingival index, probing depth and clinical attachment level comparing between hypertensive and non-hypertensive groups.

Secondary outcome (s):

- Biochemical evaluation of GCF levels of Endocan and TNF- α in hypertensive and healthy subjects by ELISA.
- Systolic and Diastolic Blood pressure measurements before and after NSPT in hypertensive vs healthy individuals and check if NSPT reduces SBP and DBP.

Clinical Relevance:

To understand the role of NSPT in stabilizing the periodontal condition as well as reduce GCF levels of Endocan and TNF- α which will subsequently result in better hypertension control and improve the lifestyle.

V. Hypothesis:

Hypertension influences response to NSPT and GCF levels of Endocan and TNF- α .

VI. Ethical considerations

•Risk and discomfort of patients: This research will be conducted with considerations of patients' safety and with attempts to reduce patients' discomfort by reassurance.

•Minimization of the risk: Patients' baseline vitals will be taken before any clinical intervention to ensure patients' safety. Moreover, all medical operations will be conducted under standardized infection control

procedures.

- **Criteria for Discontinuation of Study/patient:** Patients will be allowed to leave the study if he/ she didn't conform with the oral hygiene instructions, this will be ensured by 2 weeks, 4 weeks and 6 weeks follow-up after NSPT and assessing clinical parameters like Plaque index (PI) to determine how compliant is the patient with oral hygiene instructions. Patients with PI 2 will be eliminated. Patients with uncontrolled hypertension (SBP greater than or equal to 140mmHg and DBP greater than or equal to 90mmHg) will be eliminated.
- **Benefits to the Patients and to the Community:** Patients will receive NSPT and oral hygiene instructions with no cost. The community will benefit from this study by having a better diagnostic modality for moderate cases of periodontitis and preservation of dentition. NSPT is expected to improve patients' oral/overall health and quality of life and to be of relevance in the management of patients with hypertension.
- **Privacy:** All patients' identification including patient data and photographs will be locked and not shared.
- **Confidentiality:** Patient's data will be treated with utmost confidentiality. No personnel other than the researchers will have access to the patients' data.
- **Data Management:** All patients' data will be saved on researcher's personal laptop that are not connected to any internet connections and no copies will be made in any kind of database.
- **Consent Procedures if Applicable:** Any medical procedures and photographs will have a printed written consent form.
- **Patient Informed Consent Form:** A proper consent form will be formulated & signed by the patient before starting any procedure.

VII. Study Design:

Case-control study.

VIII. Materials and Methods:

- **Study Setting:** Faculty of Dentistry, Ain Shams University.
- **Sample Size Calculation:**

A power analysis was designed to have adequate power to apply a two-sided statistical test of the null hypothesis that there is no difference would be found between tested groups regarding clinical evaluation. By adopting an alpha (α) level of (0.05), a beta (β) of (0.2) (i.e., power=80%) and an effect size (d) of (1.53) calculated based on the results of a previous study; the total required sample size (n) was found to be (26) cases. Total sample size was increased by (25%) to account for possible dropouts during follow-up intervals to be (34) cases (i.e., 17 cases per group). Sample size calculation was performed using G*Power version 3.1.9.7. Increase to 20 cases per group to compensate for dropouts. (28)

- **Eligibility criteria:**

Inclusion Criteria

1. Patients with stage II periodontitis and controlled hypertension (self-reported history of a diagnosis of HTN by a physician and blood pressure (SBP < 140 and DBP < 90).
2. Both genders aged from 30-70.
3. Minimum 20 natural teeth excluding third molars.
4. Good compliance with the plaque control instructions following initial therapy.
5. Availability for follow-up and maintenance program.

Exclusion criteria:

1. Smokers.
2. Pregnant and lactating females.

3. Patients with other systemic diseases, such as diabetes mellitus, rheumatoid arthritis and cancer.
(According to Cornell Medical Index-Health Questionnaire).
4. Patients taking antibiotic, anti-inflammatory, and immunosuppressive therapy during the preceding 3 months before the start of the trial and during the study.
5. Patients who have undergone any periodontal therapy in the last 6 months.

Justification for Exclusions:

To reduce any confounding factors and bias that may affect the results of this study.

Study procedures:

1- Details of the interventions, testing and follow up:

Group Case (I):

This group will include 20 patients diagnosed with stage II periodontitis and controlled hypertension. They will receive NSPT and oral hygiene measures will be instructed following treatment.

Group Control (II):

This group will include 20 patients diagnosed with stage II periodontitis and no hypertension. They will receive NSPT and oral hygiene measures will be instructed following treatment.

Study protocol and surgical steps:

1. Before enrollment, a detailed case history will be recorded.
2. A calibrated standard aneroid sphygmomanometer. The average of 3 blood pressure values (systolic blood pressure SBP and diastolic blood pressure DBP), will be taken at 1 minute interval, this will be used in data analyses.

(2020 International Society of Hypertension Global Hypertension Practice Guidelines)

3. For all patients who are suitable for the study the following clinical evaluation parameters will be measured:
 - a) Plaque index (PI) (Silness&Löe, 1964)
 - b) Gingival index (GI) (Löe&Silness, 1963)
 - c) Probing depth (PD) (Caton, 1980).
 - d) Bleeding on probing (BOP) (Ainamo, 1985)
 - e) Clinical attachment level (CAL) (Ramfjord, 1967).
 - f) Standardized periapical radiograph. (Pananou, 2017)

Note: Full mouth assessment will be done and then the deepest site will be evaluated for the GCF sample.

4. Baseline GCF samples will be taken the day after patients were clinically evaluated to prevent contamination with blood related to the probing of inflamed areas.
5. The sample areas will be insulated with cotton rolls to prevent saliva contamination and all supragingival plaque will be eliminated. The paper strips will be placed into the periodontal pocket and then permitted to remain for 30 seconds.
6. All patients will undergo full mouth NSPT, this will be done using ultrasonic and hand instruments.
7. The patients will receive oral hygiene instructions including tooth brushing using modified bass technique. All patients will be provided with toothbrush (soft), toothpaste (signal) and interdental cleaning with dental floss or interdental brush.
8. Two weeks follow-up to ensure that appropriate oral hygiene instructions are followed. The clinical parameter to be assessed will be PI and BOP, patients with PI 2 and BOP $> 10\%$ will be eliminated from the study.
9. Then clinical evaluation, collection of samples and measuring of SBP and DBP will be performed at 3 months after NSPT in both groups.

Outcomes Assessment:

- Clinical assessment.
- Biochemical assessment.
- Blood pressure measurement.

For clinical assessment the following clinical parameters including PI, GI, PD, BOP and CAL will be recorded for each individual at 1 site at baseline and 3 months postoperatively. Clinical parameters of PI and BOP will be assessed at 2 weeks, 4 weeks and 6 weeks follow ups to ensure proper oral hygiene. Regarding biochemical analysis, GCF samples will be collected preoperative and 3 months after NSPT. Blood pressure measurements will be taken before and after 3 months of NSPT.

a) Clinical Assessment

The following clinical parameters will be taken using UNC15 Probe at baseline and 3 months postoperative.

- **Plaque index: - (Loe and Silness ,1963)**
0 = no plaque.
1 = plaque recognized only by running a probe across the tooth surface.
2 = plaque visible to the naked eye.
3 = abundance of soft matter.
- **Gingival index: -(Loe and Silness ,1963)**
0 = Normal gingiva
1 = Mild inflammation – slight edema. No bleeding on probing
2 = Moderate inflammation -redness, edema and glazing.
Bleeding on probing.
3 = Severe inflammation – marked redness and edema.
Ulceration. Tendency for spontaneous bleeding
- **Probing depth : (Ramfjord, 1959)**
Will be measured from the gingival margin to the depth of the pocket at four points (mesio-facial, mid-facial, disto-facial and mid-lingual) to the nearest millimeter using UNC-15 periodontal probe The average of the three facial points will be recorded as the facial probing depth (FPD), while the mid-lingual point will be recorded as the lingual probing depth.
- **Clinical attachment level (CAL):(Ramfjord et al., 1975).** Will be measured from the CEJ to the depth of the periodontal pocket.

b) Biochemical Assessment:

Biochemical assessment will be done at the deepest pocket at baseline, and 3 months after non-surgical periodontal therapy. Endocan and TNF- α levels will be determined using commercial human Endocan (ESM-1) and TNF- α ELISA Kits. Measurements will be performed according to the manufacturer's instructions.

c) Blood Pressure measurement:

Blood pressure measurement will be done according to, 2020 International Society of Hypertension Global Hypertension Practice Guidelines.

IX. Statistical Analysis

The obtained results will be collected, tabulated, and subjected to appropriate statistical analysis.

X. Funding of the Study

This study will be personally funded by the researcher.

References:

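### The total of 26 does not follow from d = 1.53, two-sided alpha 0.05 and 80% power for any single-parameter t or rank test, and the protocol does not say which of its four unranked primary parameters d refers to

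*Protocol*

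**What the plan says.** Section IV (Primary outcome) gives four parameters, compared between the two groups: "Clinical evaluation of periodontal parameters plaque Index, gingival index, probing depth and clinical attachment level comparing between hypertensive and non-hypertensive groups". None is ranked above the others.

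The opening summary (Materials and Methods) lists the same four: "plaque index, gingival index, probing depth, clinical attachment level (CAL) as primary outcome". There the closing phrase could attach to the whole list or to CAL alone.

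The PICOTS table in section III names no parameter. Its outcome row says "Clinical evaluation as a primary objective" and its time row says "Baseline and 3 months (for clinical evaluation".

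The Sample Size Calculation in section VIII sizes the study on a single two-sided comparison, whose hypothesis is worded as "null hypothesis that there is no difference would be found between tested groups regarding clinical evaluation". It gives alpha 0.05, beta 0.2 and "an effect size (d) of (1.53) calculated based on the results of a previous study", and concludes that "the total required sample size (n) was found to be (26) cases". A 25% allowance raises this to 34, and a further allowance for dropouts raises it to 20 per group.

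**The concern.** There are two linked problems.

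- **The arithmetic.** An effect size d with a two-sided test and equal groups describes a two-sample comparison of means. At d = 1.53 that comparison needs far fewer than 26 patients for 80% power, so at least one of the printed figures is not the one that was used.
- **The target.** There is one null, one alpha, one d and one power figure, but four primary parameters. Two are 0-to-3 scores (plaque and gingival index) and two are in millimetres (probing depth and CAL), and they need not share one standardised effect. A reader cannot tell which of them the 80% power describes, nor which result answers the primary question.

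At stake is whether the sample-size justification can be checked, and whether the primary comparison is fixed before the data are seen. The safety of the planned enrolment at the protocol's own d is not in question.

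**Working it through.** **Inputs, all from section VIII:** d = 1.53; two-sided alpha 0.05; power 80%; equal groups; stated total 26 (13 per group); planned enrolment 20 per group.

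**1. Trying to reproduce 26.**

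Normal approximation: n per group = 2(z₀.₉₇₅ + z₀.₈₀)²/d² = 2(1.960 + 0.842)²/1.53² = 6.7, so 7 per group, 14 in total.

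Exact two-sample t-test: power comes from the noncentral t distribution with 2n − 2 degrees of freedom and noncentrality d√(n/2). For n = 8 the noncentrality is 1.53 × √4 = 3.06 and the critical value is 2.145.

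| n per group | Total | Power at d = 1.53, alpha 0.05 |
|---|---|---|
| 7 | 14 | 74.8% |
| 8 | 16 | 81.2% |
| 12 | 24 | 94.7% |
| 13 | 26 | 96.2% |
| 20 | 40 | 99.7% |

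The smallest total reaching 80% is 16. The stated 26 is not reproduced.

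**2. Other single-parameter readings at alpha 0.05 and 80% power.** A Wilcoxon-Mann-Whitney test, sized by relative efficiency, needs 18 (efficiency 0.955, normal data) or 20 (efficiency 0.864, the minimum). A one-sided t-test needs 14. A paired or one-sample t-test needs 6. None gives 26.

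**3. What 26 would correspond to.** With the t-test at alpha 0.05, 26 is the smallest equal-group total that reaches 95% power at d = 1.53 (24 gives 94.7%). Equally, it is the total for 80% power at d of about 1.15.

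**4. The later steps.** 26 × 1.25 = 32.5, which becomes 34 when rounded up to equal groups with a margin of one pair at most. The unexplained step is therefore the 26, not the inflation.

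**5. If all four parameters stay primary with Bonferroni.** Alpha per test is 0.05/4 = 0.0125. At d = 1.53, 11 per group gives 79.0% and 12 per group gives 83.6%, so the total for 80% power is 24. The loss of power per test is:

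| Evaluable per group | Alpha 0.05 | Alpha 0.0125 |
|---|---|---|
| 13 | 96.2% | 87.4% |
| 20 | 99.7% | 98.4% |

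The loss grows if the true d is smaller. As an illustration only, at an assumed d of 0.8 with 20 per group, power falls from 69% to 47%.

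**6. The any-of-four case, for reference.** If any one of four independent tests at 0.05 counted as success, the false-positive rate would be 1 − 0.95⁴ = 18.5%. It would be lower with correlated outcomes: about 16% at an assumed pairwise correlation of 0.5 and 10% at 0.9 (simulated t-tests, 20 per group). The protocol gives no correlations and states no such rule.

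**The case against.** **The protocol names no test, so 26 may come from another one.** This stands in part. A four-variable Hotelling T² test, with 1.53 read as a Mahalanobis distance, has 76.1% power at 12 per group and 80.8% at 13, which gives 26. But the protocol mentions no multivariate test, and a two-sided test with effect size d does not describe one. A rank test at minimum efficiency and alpha 0.0125 also gives 26, but that contradicts the stated alpha of 0.05. The arithmetic claim is therefore limited to single-parameter t or rank tests at 0.05. That one sentence can yield 16 or 26 depending on an unnamed test is itself a reason to name it.

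**The error is harmless.** At the protocol's own d this is right: 26 exceeds both the 16 needed at 0.05 and the 24 needed at 0.0125. A reader might infer that the study is underpowered, but the documents do not support that.

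**Multiplicity rules belong in the analysis plan.** This also stands. A reader might infer a false-positive rate of up to 18.5%, but that needs an any-of-four success rule. The protocol does not state one, and an analysis plan that is not shown could settle the matter. What remains the protocol's own task is to say which parameter its single null and its sample size concern.

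**The source cited as (28) may identify the parameter.** It may. No entry 28 is legible in the extracted reference list, so the claim is only that the sample-size text does not name the parameter.

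**Conclusion.** The point holds in a limited form and should be fixed. For any single-parameter t or rank test at two-sided 0.05, the stated d, power and n cannot all be right: the inputs give 16 (t-test) or about 18 to 20 (rank test), against a stated 26. Under the t-test, 26 carries 96.2% power at d = 1.53, or 80% at d of about 1.15. The discrepancy errs towards more patients.

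Separately, the text ties neither the single null nor d = 1.53 to any of the four unranked primary parameters, and the opening summary leaves open whether CAL alone is meant. The power of the study for a given primary parameter therefore cannot be checked.

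The power figures assume equal groups, a t-test unless stated otherwise, and that d = 1.53 applies to the parameter tested. The documents do not allow that last assumption to be verified.

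**What to change.** 1. Name one primary parameter and its measure (the 3-month value or the change from baseline), and make the other three secondary. Use the same wording in the opening summary, the PICOTS table, section IV and the Sample Size Calculation. CAL is a reasonable candidate, but the choice is the sponsor's.
2. State the parameter and the test behind d = 1.53.
3. Restate the sample-size paragraph so that d, alpha, power, test and n agree. With a t-test at d = 1.53 and two-sided 0.05, that is 16 in total for 80% power, or about 96% power for 26. If a different d or a multivariate test was used, say so.
4. If all four are to remain primary, state the rule, for example Holm, or Bonferroni at 0.0125 (24 in total at d = 1.53 and 80% power).

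**Cost.** Naming one parameter costs wording and a recalculation, and three parameters lose primary status. It needs no new data and, at the protocol's d, no more than the planned 20 per group. Under Bonferroni, power per test falls from 96.2% to 87.4% with 13 evaluable per group, or from 99.7% to 98.4% if all 20 are evaluable. The loss is larger if the true d is smaller.

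### Two differing post-treatment rules on plaque index and bleeding decide who is compared at 3 months, although plaque index is itself a primary outcome

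*Protocol*

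**What the plan says.** Four places in the protocol bear on who stays in the study after non-surgical periodontal therapy (NSPT).

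- **Section VI, criteria for discontinuation.** Oral hygiene compliance is checked after treatment: "this will be ensured by 2 weeks, 4 weeks and 6 weeks follow-up after NSPT". The consequence is "Patients with PI 2 will be eliminated". No bleeding condition is attached.
- **Section VIII, study protocol and surgical steps, step 8.** This describes a 2-week follow-up: "The clinical parameter to be assessed will be PI and BOP, patients with PI 2 and BOP" above 10% are eliminated from the study. Weeks 4 and 6 are not named.
- **Section VIII, outcomes assessment.** "Clinical parameters of PI and BOP will be assessed at 2 weeks, 4 weeks and 6 weeks follow ups to ensure proper oral hygiene". No threshold or consequence is given.
- **Section VIII, inclusion criterion 4.** Good plaque-control compliance after initial therapy is an entry condition, although it can only be judged once treatment has been given. It is not tied to either rule.

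The primary outcome in section IV is "Clinical evaluation of periodontal parameters plaque Index, gingival index, probing depth and clinical attachment level comparing between hypertensive and non-hypertensive groups". The outcomes assessment says these measures "will be recorded for each individual at 1 site at baseline and 3 months postoperatively". The hypothesis in section V begins "Hypertension influences response to NSPT and GCF levels of Endocan".

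**The concern.** The first problem is the contradiction. Two investigators who each follow the protocol could keep different patients.

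The second problem is what the rule acts on. Both versions select on PI, alone or with BOP, measured after treatment and before the 3-month comparison. PI is one of the four listed primary outcomes, and the study hypothesis is that the exposure changes the response to treatment. A patient's presence in the comparison may therefore depend on something the exposure affects. If so, the patients retained in the two groups are no longer comparable in the way the enrolled patients were.

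The main question is who is compared. A loss of numbers is secondary.

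**Working it through.** **1. The rules side by side**

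| | Section VI | Step 8 | Outcomes assessment |
|---|---|---|---|
| Score | PI 2 | PI 2 and BOP above 10% | none |
| Visits named | weeks 2, 4, 6 | week 2 | weeks 2, 4, 6 |
| Consequence | eliminated | eliminated | none stated |

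Week 2 is common to all three, so the visit schedules differ in extent and are not disjoint. The criteria already differ at week 2:

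- If *and* in step 8 means both signs, a patient with PI 2 and BOP of 10% or less is removed under section VI and kept under step 8.
- If it means either sign, a patient with BOP above 10% without PI 2 is removed under step 8, while section VI states no rule for that patient.
- On both readings, PI 2 first seen at week 4 or 6 is covered explicitly only by section VI.
- Neither place says whether PI 3 is included.

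The sites are also open. A percentage cut for BOP implies many sites, and a note in the procedures says "Full mouth assessment will be done and then the deepest site will be evaluated for the GCF sample". The outcome measures are recorded at one site, and the sites for the PI check are not stated. How closely the check tracks the outcome PI is therefore unknown.

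**2. How many patients the conflict could touch**

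The protocol gives no rates. Assumptions: 10% of patients show PI 2 at any one visit, 50–80% of those also have BOP above 10%, and the correlation between visits is 0.5–0.8.

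- Week 2 alone, both signs: 10% × (20–50%) = 2–5%, or 0.8–2.0 of 40 patients treated differently.
- Section VI over three visits (PI 2 at any visit, multivariate normal): 17.2–21.8%, or 6.9–8.7 of 40 removed.
- Step 8, both signs, week 2 only: 10% × (50–80%) = 5–8%, or 2.0–3.2 of 40 removed.
- Treated differently if step 8 is the only check: 17.2% − 8% = 9.2% up to 21.8% − 5% = 16.8%, or 3.7–6.7 of 40.
- Step 8, either sign, if 20–30% of all patients have BOP above 10%: 10% + 20% − 8% = 22% up to 10% + 30% − 5% = 35%, or 8.8–14.0 of 40 removed.

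**3. What selection could do to the contrast**

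An illustrative model has a check score S and a 3-month outcome Y, both with SD 1 and higher meaning worse, with correlation r = 0.3–0.7. The 3-month group difference is the protocol's d = 1.53. Hypertension shifts S by k × d. The cut removes 15% or 30% of controls.

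Among retained patients, the mean of S lies below its group mean by φ(z)/Φ(z), where z is the cut minus the group mean. The change in the 3-month contrast is r times the difference between the groups in that quantity.

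Worked case (k = 0.3, 15% of controls removed, r = 0.5):

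- Cut = 1.036; shift = 0.3 × 1.53 = 0.459; z for hypertensives = 0.577.
- Hypertensives removed: 1 − Φ(0.577) = 28.2%.
- Displacement of S: −0.274 in controls, −0.470 in hypertensives.
- Change in contrast: 0.5 × (−0.470 + 0.274) = −0.098.
- Share kept: (1.53 − 0.098)/1.53 = 93.6%.

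| Shift of check score | Hypertensives removed, of 20 | Change in contrast (SD) | Share of d = 1.53 kept |
|---|---|---|---|
| 0 | 3.0 or 6.0 | 0 | 100% |
| 0.3 × d | 5.6 or 9.5 | −0.06 to −0.18 | 88–96% |
| 0.5 × d | 7.9 or 11.9 | −0.11 to −0.32 | 79–93% |

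The change does not depend on the true 3-month difference. If there is no true difference but the check score is shifted by the same amount, the same −0.06 to −0.32 SD appears as a false advantage for hypertensives.

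**4. Against the dropout allowance**

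The sample size section plans 20 per group against 13 required (26 in total), an allowance of 7 per group. With no shift, 3.0 or 6.0 hypertensives are lost and the allowance covers it. With a shift, the losses are 5.6, 9.5, 7.9 and 11.9, so three of the four cases exceed it. Power at d = 1.53 is 99.7% with 20 per group and 96% with 13 per group. In simulated trials under the selection model it stays at about 84% or more.

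**The case against.** **Compliers may be the intended population.** Inclusion criterion 4 and the discontinuation criteria suggest that a compliant population is wanted, and response among compliers is a legitimate, narrower question. That stands, and with no effect of hypertension on the check score the contrast is not biased. It does not excuse two definitions of the population, nor selection on an early value of a primary outcome.

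**Step 8 need not exclude later checks.** It names week 2 without saying that this is the only check. This also stands. If the later checks apply too, the both-signs count falls towards the week-2 figure of 0.8–2.0 of 40, but the criteria still differ at week 2. Section VI also cites PI as an example of the parameters assessed, so one cannot say that it positively keeps a patient with BOP above 10%. The either-sign counts are therefore the weakest.

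**The SAP could define analysis sets.** It could, but it would not reconcile two protocol rules or recover measurements that were never taken.

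A reader might also infer the following, which the document does not support:

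- *The bias is toward no difference.* This holds only if hypertension also worsens the 3-month outcome. With four primary outcomes, one direction cannot be claimed for all. No passage says that hypertension worsens early plaque or bleeding.
- *The losses fit the allowance, or the trial becomes underpowered.* Neither is shown. Coverage depends on unstated rates, and power at the planned effect stays high.
- *Eliminated patients certainly have no 3-month data.* That is the natural reading of elimination from the study, but the protocol does not state it, and section VI also speaks of patients being allowed to leave.

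**Conclusion.** The concern holds in this form. The protocol states the post-treatment elimination rule in two ways that differ at week 2 and in the later visits they name, and the outcomes assessment does not settle it. Because the rule uses PI, a listed primary outcome, the set of patients compared at 3 months depends on an early post-treatment value.

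Whether this biases the comparison depends on whether hypertension affects early PI or BOP, which the protocol does not say. If it does, the contrast shrinks where the 3-month outcome is also worse in hypertensives, and a false difference in their favour can appear where it is not. If it does not, the result is unbiased but applies to compliers only.

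The contradiction rests on the text alone. Every size given above is illustrative: it rests on assumed PI 2 and BOP rates, assumed correlations and an assumed shift of the check score. This should be fixed before patients are removed under either rule.

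**What to change.** 1. Reconcile the discontinuation criteria in section VI, step 8, the outcomes assessment and inclusion criterion 4 into one definition of non-compliance. It should state the scores (including whether PI 3 counts), whether both signs or either is needed, the visits and the sites.
2. Use that definition to classify compliance, not to remove patients. Record the 2-, 4- and 6-week scores as compliance data, keep every treated patient to the 3-month visit, and include them in the primary comparison.
3. Report the compliant subset as a sensitivity analysis.

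The cost is protocol wording only, since all these visits are already planned. The downside is that less compliant patients somewhat dilute the average response; the sensitivity analysis shows by how much.

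Elimination for uncontrolled hypertension in section VI is a separate rule and is not addressed here.
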